**FRED HUTCHINSON CANCER RESEARCH CENTER
UNIVERSITY OF WASHINGTON SCHOOL OF MEDICINE**

**Personalized radiation therapy through functional lung avoidance and
response-adaptive dose escalation: utilizing multimodal molecular
imaging to improve the therapeutic ratio (FLARE RT)**

Principal Investigator: [name]
Associate Professor
Department of Radiation Oncology
University of Washington Medical Center
[name]
[name]
[contact]
[contact]
Email: [contact]

Co-Investigators: [name]
[name]
[name], PhD
[name]

Version date:

Protocol Amendment 4: version February 5, 2020

Study Summary

Title	Personalized radiation therapy through response-adaptive dose escalation and functional lung avoidance: utilizing multimodal molecular imaging to improve the therapeutic ratio (FLARE RT)
Short Title	FLARE RT
Protocol Number	CCIRB 9599
Phase	Phase II
Methodology	Single Arm Open-Label
Study Duration	5 yrs.
Study Center(s)	University of Washington Medical Center
Objectives	To utilize mid-treatment FDG PET/CT tumor response to select non-responding patients for dose escalation, while utilizing functional lung avoidance to mitigate toxicity. Changes in tumor FDG uptake on mid-treatment PET/CT (24 Gy nominal) will divide patients into “responders” and “non-responders”. Responders will receive 60 Gy to their tumor per standard of care; non-responders will undergo dose escalation to 74 Gy. All patients will receive functional lung avoidance radiation treatment via SPECT/CT imaging with ^{99m}Tc-MAA and ^{99m}Tc-SULFUR COLLOID to accurately identify and preferentially spare functional lung. Primary endpoint of this study will be 2-yr. overall survival.
Number of Subjects	The projected enrollment number is 60 in order to meet the study goal of 50 evaluable subjects.
Diagnosis and Main Inclusion Criteria	Patients diagnosed with stage IIB-III non-small cell lung cancer receiving definitive chemoradiation.
Study Product, Dose, Route, Regimen	All scans are FDA approved for use with patients: ^{18}FFDG-PET/CT and SPECT/CT with ^{99m}Tc-MAA and ^{99m}Tc-Sulfur Colloid
Duration of administration	Beyond standard of care imaging, some patients may undergo a repeat baseline protocol specific FDG-PET/CT, and be considered research, then a PET/CT mid-treatment, and 2 SPECT/CT scans (pre-treatment and 3 months post-treatment).

Statistical Methodology	Primary endpoint of the study will be 2 yr. overall survival, compared to the 60 Gy cohort of RTOG 0617 (57% 2yr OS). With an estimated improvement to 72% 2yr OS, we will need 49 patients to test for superiority of FLARE RT at 80% power and 5% Type I error. Secondary endpoints will include toxicity, and in particular CTCAE v4 grade 2 or higher pneumonitis, and 1 yr. local control, progression-free survival, and pulmonary function test decline. We will also collect plasma and urine for future correlative studies.
-------------------------	--

Table of Contents

1. Introduction
 - 1.1. Background
 - 1.2. Local Control Impacts Survival in Locally Advanced NSCLC
 - 1.3. Radiation Dose Escalation Can Improve Local Control in NSCLC, but Uniform Dose Escalation Is Detrimental
 - 1.4. FDG PET/CT Can Select For Patients at High Risk of Local Failure and Guide Dose Escalation
 - 1.5. Radiation to the Lungs Causes Pulmonary Toxicity and Limits the Deliverable Dose
 - 1.6. Current Radiation Planning Methods are Unable to Accurately Predict Which Patients Will Develop Pulmonary Toxicity
 - 1.7. SPECT/CT Perfusion/Ventilation Scans can Detect Heterogeneity in Lung Function
2. Study Objectives
3. Study Design
 - 3.1. General Design
 - 3.2. Statistical Plan
 - 3.3. Eligibility
4. Study Registration
5. Radiation Therapy
 - 5.1. Dose Specifications
 - 5.2. Localization, simulation and immobilization
 - 5.3. Target Volumes
 - 5.4. Critical Structures
 - 5.5. Treatment Planning
 - 5.6. Radiation Quality Assurance Reviews
 - 5.7. Radiation Toxicity
 - 5.8. Criteria for Removal/Withdrawal from Treatment
6. Systemic Therapy
7. Data and Safety Monitoring Plan
 - 7.1. Early Stopping Rules
 - 7.2. Interim Data Review
8. Data Management/Confidentiality

1 Introduction

This document is a protocol for a human research study. This study is to be conducted according to US and international standards of Good Clinical Practice (FDA Title 21 part 312 and International Conference on Harmonization guidelines), applicable government regulations and Institutional research policies and procedures.

1.1 Background

Radiation is a major treatment option for patients with locally advanced non-small cell lung cancer (NSCLC), but current treatment regimens result in suboptimal tumor control with local failures up to 50% and 5-year overall survival (OS) of 10-20%, while carrying substantial risk of toxicity, with grade 3+ pulmonary toxicity seen in approximately 20% of patients (1-4). We propose to improve the therapeutic ratio by limiting pulmonary toxicity risk through radiation dose avoidance of functional lung defined on ventilation/perfusion SPECT/CT and increasing local control through FDG-PET/CT guided tumor dose escalation in select patients at high risk of local failure. We will explore several questions with clinical significance: (1) whether the combination of selective tumor dose escalation and functional lung avoidance synergistically impacts patient outcomes, (2) whether patient selection based on early FDG PET response can improve the potential survival benefit from PET-guided dose escalation, (3) whether radiation dose burden to functional lung better predicts clinical lung toxicity than radiation dose burden to anatomic lung, and (4) whether image parameters of spatial and functional heterogeneity in lung can select patients prior to treatment who are at highest risk of pulmonary toxicity. Answers to such questions within the scope of this pilot trial will support the launch of a multi-center trial that can definitively assess the efficacy of FLARE RT. Development of functional lung imaging heterogeneity tools and FLARE RT planning tools will enable radiation oncologists and radiologists to more precisely manage and deliver care to cancer patients.

1.2 Local Control Impacts Survival in Locally Advanced NSCLC

Although current treatments have dose limiting toxicities including pulmonary toxicity, local control after radiation treatment is still suboptimal at around 50%. When patients die from NSCLC, both metastatic sites of disease and disease in the chest contribute to the causes of deaths (5). The lack of local control of lung tumor is clearly correlated with worse survival, and the death-rate for patients with intra-thoracic disease recurrence is similar to death-rate for patients with metastatic disease (6-8). In the CHART randomized trial testing different radiation dose/fractionation schemes, improving the local control from 20% to 29% resulted in improvement in median survival from 10 months to 28 months (9). Therefore, local control of lung tumors does impact the overall survival in patients with locally advanced lung cancer.

1.3 Radiation Dose Escalation Can Improve Local Control in NSCLC, but Uniform Dose Escalation Is Detrimental

Dose-escalation studies have shown promising local control rates when radiation dose is escalated above the standard 60 Gy in conventional fractionation. One study looking at 122 patients receiving definitive radiation treatment for lung cancer, without surgery, found that each 1 Gy increase in dose resulted in approximately 1.25% improvement in

5-year local control (3). For patients treated to 63-69 Gy, 5-year local control was 12%, versus 49% for patients treated to >90 Gy. The same trend is seen for 5-year OS, 4% versus 28% for the lower dose versus higher dose groups, respectively. Analysis of multiple patient series has found that a 1 Gy increase in dose leads to 3-4% improvement in survival and local control (10).

The potential survival advantage from dose escalation beyond 60 Gy was tested in a randomized trial in RTOG 0617, where patients with locally advanced NSCLC were treated to 60 Gy versus 74 Gy (11). Surprisingly, results showed that uniform dose escalation to the entire tumor volume in all patients is inferior to standard dose radiation. Local control and OS were worse in the 74 Gy arm versus the 60 Gy arm. Exact cause of the inferior outcome in the higher dose arm is unclear, but higher heart radiation dose was found to be associated with worse outcomes, and heart dose was higher in the 74 Gy arm compared to the 60 Gy arm. It is unknown if the higher heart dose is truly the cause of increased mortality, or a surrogate marker for other poor prognostic variables that were unbalanced between the two randomized arms. For example, multiple surgical series have found subcarinal lymph node involvement and multi-station mediastinal nodal involvement to be associated with poor survival in patients in lung cancer (12-14). The same effect is seen in patients treated with chemoradiation (15). Both subcarinal disease and multi-station nodal disease are associated with higher radiation dose to the heart (16). Therefore, it is possible that the higher heart dose in the higher dose arm is a surrogate for mediastinal nodal involvement, which is well known to have a negative impact on survival.

These results highlight the importance of selecting the right patient population for dose escalation, since not all patients experience local failures after 60 Gy, and only patients who would have experienced local failure would potentially benefit from escalated radiation dose beyond 60 Gy. Giving more radiation dose uniformly across an entire patient population will likely cause as much toxicity as benefit; therefore it is key to utilize strategies that can identify patients at high risk of local failure after conventional radiation doses of 60 Gy.

1.4 FDG PET/CT Can Select For Patients at High Risk of Local Failure and Guide Dose Escalation

Given that up to 50% of patients with NSCLC develop local recurrences after standard radiation treatment, methods to improve local control are needed. However, randomized data have shown that dose escalation in all patients leads to worse outcomes when looking at the entire patient population (11). Strategies to identify patients at high risk of local failure are needed to target therapy intensification in the group of patients who will benefit. High tumor uptake on mid-radiation treatment FDG PET relative to baseline FDG PET is associated with poorer clinical outcomes, and local recurrences after radiation treatment tend to occur inside FDG PET avid regions (17-19). It has been estimated that 60% of patients were classified as early non-responders on FDG PET and that this subpopulation had overall survival rates of 33% compared to 92% in the responder subpopulation (van Elmpt, Ollers, et al. 2012). This result highlights both the prevalence of poor tumor response early during treatment and its significant impact on patient outcomes. Further, high spatial correlation between FDG PET avid areas and

recurrent disease (20, 21) help refine the definition of high-risk treatment targets in NSCLC.

Ongoing clinical trials are defining targets on FDG PET/CT for concomitant dose escalation but do not select patients according to local failure risk. The PET boost trial in the Netherlands utilizes discrete dose escalation to FDG PET avid regions (50% SUV_{max} threshold) based on pre-treatment assessment and individualizes integral target dose boosts based on mean lung dose, but does not account for patient variability in early treatment response (22). RTOG 1106 is investigating whether tumor dose can be escalated to improve the local control rate based on FDG-PET/CT imaging at 40-46 Gy during treatment, which exploits higher achievable dose escalation following tumor volume regression (17). This adaptive dose escalation trial design to concurrently boost residual FDG PET avid regions late in therapy poses the following challenges: (1) potential for increased toxicity with little survival benefit from dose escalation in patients whose tumors have already responded to standard dose radiation therapy, (2) limited radiobiological effectiveness with 9/30 radiation treatment fractions available for dose escalation during accelerated tumor cell repopulation, and (3) enhancement of radiation-induced inflammatory response signal on late mid-therapy FDG PET/CT imaging that can confound target definition.

Patients at high local failure risk can be selected according to the quantitative change in tumor FDG PET SUV_{max} and total lesion glycolysis as early as 2-3 weeks into treatment, which is predictive of clinical outcomes (23, 24). An earlier assessment of treatment response (2-3 week time point instead of waiting until 40-46 Gy during week 4-5) has the benefit of allowing earlier implementation of dose escalation to regions at high risk of local failure. The 2-3 week mid-treatment PET/CT can select for patients who are at high risk of local relapse, and treat this high risk subpopulation with dose escalation to improve cancer control, which is another step towards personalized medicine for this patient population.

1.5 Radiation to the Lungs Causes Pulmonary Toxicity and Limits the Deliverable Dose

When improving the therapeutic ratio, dose escalation must always be weighed against potentially increased toxicity. Radiation to the lungs cause a spectrum of changes, with the two most clinically relevant changes being radiation pneumonitis (RP) and radiation induced fibrosis. Radiation pneumonitis is a disorder characterized by inflammation focally or diffusely affecting the lung parenchyma. It occurs in the subacute phase after radiation treatment, from several weeks to several months after completion of therapy. Radiation pneumonitis can be mild, causing shortness of breath that does not require intervention and resolves spontaneously, to severe, requiring steroids, oxygen, ventilation, or, if not treatable even, even death. Radiation pneumonitis is a dose-limiting toxicity in lung cancer treatment, causing worsening respiration in patients who often already have underlying lung disease, such as emphysema. Approximately 15-40% of patients develop clinically significant radiation pneumonitis after treatment with conventional radiation doses (25). Long term, lung tissue treated with radiation can develop fibrosis, and is no longer able to function in gas-exchange. This can lead to a permanent reduction in pulmonary function. Symptomatic lung damage is the major impediment to safely escalate dose to lung tumors.

1.6 Current Radiation Planning Methods are Unable to Accurately Predict Which Patients Will Develop Pulmonary Toxicity

Radiation pneumonitis and global pulmonary dysfunction are poorly predicted by current radiation planning methods, which consider all lung tissue to be equally important in pulmonary gas exchange (and equally vulnerable to radiation damage). Mean radiation dose to the lung (mean lung dose=MLD) and percent of lung volume receiving at least 20 Gy of radiation (V20) are the two most commonly used metrics for estimating risk for developing pulmonary toxicity from radiation treatment. Many other studies have tried to incorporate other variables into prediction models for radiation pneumonitis and global dysfunction, including clinical parameters as well as radiation treatment plan parameters, but the most widely used metrics for evaluating a radiation treatment plan are still MLD and V20. In a recent large international series of 836 patients, V20 was found to be predictive of radiation pneumonitis: 18% of patients receiving $V20 < 20\%$ (lowest lung dose group) developing symptomatic RP, 0% fatal; versus 30% symptomatic RP in the V20 between 20-30% patient group (intermediate lung dose group but still within V20 that is typically considered safe) and 1% fatal RP; versus the highest lung dose group with $V20 > 40\%$, developing 36% RP and 3.5% fatality (25). This data emphasizes that even in the lowest lung dose group (according to V20), almost 20% of patients are still developing radiation pneumonitis; and even in the highest lung dose group, more than 60% of patients do not develop RP. This calls for a better method of predicting RP than the current parameters of MLD and V20.

1.7 SPECT/CT Perfusion/Ventilation Scans can Detect Heterogeneity in Lung Function

Current standard practice in radiation oncology, relying on MLD and V20 to quantify lung dose, treats all lung tissue as if it functions equally. In reality, lung tissue function is spatially heterogeneous, especially in patients with baseline lung disease such as smoking-induced COPD where ventilation and perfusion-mediated gas exchange becomes compromised. Perfusion and ventilation SPECT/CT imaging using ^{99m}Tc -labeled MAA and SULFUR COLLOID, respectively, is commonly performed as a non-invasive diagnostic imaging test of pulmonary function, is utilized by surgeons to predict post-operative lung function, and has strong potential for use in RT planning (26). Conventional RT planning based on anatomic lung dose constraints yielded large variability in dose to functional lung across patients (27) that can be accounted for in functional avoidance planning. Prior studies using planar scintigraphy and MAA SPECT perfusion scans with long-term follow-up provided strong rationale for modeling regional perfusion reduction as a function of delivered radiation dose (28, 29). Independent investigations were able to link perfusion SPECT-weighted dose to post-RT pulmonary toxicity (30, 31). However, no link was established between regional perfusion deficits and pulmonary toxicity in part due to existing technical limitations in spatial resolution and quantitative accuracy that are now achievable with modern SPECT/CT imaging techniques (32). The technical feasibility of incorporating lung function imaging heterogeneity into treatment planning has been well-established (33-37) and can be readily implemented once an imaging surrogate for radiation-induced pulmonary toxicity risk is identified.

The established clinical utility and widespread availability of perfusion and ventilation imaging using ^{99m}Tc-labeled MAA and SULFUR COLLOID SPECT/CT, respectively, make this approach most feasible for eventual incorporation of functional lung avoidance into routine radiation oncology practice.

2 Study Objectives

Primary Objective

The primary endpoint of the study will be 2 year overall survival. The primary objective will be to test the superiority of 2yr OS in the FLARE RT patient cohort over the 60 Gy cohort of RTOG 0617 (57% 2yr OS) for historical control. Based on an estimated improvement to 72% 2yr OS, we will enroll at least **49 patients** to test for superiority of FLARE RT at 80% power and 5% Type I error.

Secondary Objective

[figure not shown]
- CTCAE v4 grade 2 or higher pneumonitis incidence from FLARE RT compared to historical controls (non-inferiority test)
- 1 yr local control, progression-free survival, and pulmonary function test decline
- Identification of baseline FDG PET/CT and mid-treatment FDG PET/CT imaging biomarkers for predicting patient survival
- Identification of baseline perfusion SPECT/CT imaging biomarkers for predicting G2+ pneumonitis and PFT decline
- Collection of plasma and urine samples for future correlative studies between imaging biomarkers and cytokine biomarkers of radiation response in both tumor and normal tissue

3 Study Design

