3.2. Statistical Plan

The primary endpoint of the study will be 2-year overall survival (OS). The primary objective will be to test the superiority of the 2-year overall survival rate in patients enrolled on the FLARE RT trial compared to the 60 Gy cohort of RTOG 0617 (57% 2yr OS) for historical control (11). RTOG 0617 was a randomized phase III trial for patients with unresectable non-small cell lung cancer (NSCLC), testing two radiation doses (60 Gy versus 74 Gy), and addition of cetuximab to standard chemoradiation. Results of RTOG 0617 established the current standard of care for NSCLC: concurrent chemoradiation to 60 Gy.

The expected 2yr OS and effect size of FLARE RT was derived from a weighted average of mid-treatment FDG PET responders (2 yr. OS = 92%, 41% of patient population) and non-responders (2 yr. OS = 33%, 59% of patient population) identified in a prospective patient series with 2 yr. OS rate (56%) in strong agreement with the 60 Gy cohort of RTOG 0617 (23). Based on data from a dose escalation meta-analysis (10) and the University of Michigan experience tumor dose escalation to 74 Gy in non-responders are expected to produce 4% relative improvement in overall survival per Gy (3). Combined with functional lung avoidance to reduce mean perfused lung dose from 20 Gy to 10 Gy and risk of clinical grade radiation pneumonitis, we predict a 72% 2yr OS in patients receiving FLARE RT.

The FLARE RT trial features a non-randomized design that selectively assigns patients to one of two arms based on early treatment response assessment on FDG PET/CT. In order to assess whether this selection strategy leads to superior 2yr OS compared to the historical control, we will perform a one sample proportionality test using all patients who complete either FLARE RT treatment arm (standard dose arm in responders + dose escalation arm in non-responders). In our cohort of at least 49 patients, the test is expected to detect a 2yr OS rate improvement relative to historical control from 57% to 72%, under assumptions of 5% Type I error rate ($\alpha=0.05$), 80% power ($\beta=0.20$), and 1% margin of superiority ($\delta=0.01$).

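### Section 2 attaches 80% power to 49 patients enrolled, although 49 is the number the primary test has to analyse and the Summary projects 60 enrolled for 50 evaluable

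*Combined protocol and SAP*

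**What the plan says.** Three places give a number of patients for the primary comparison of 2-year overall survival.

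- Section 2, Primary Objective, gives an enrolment number and ties the power to it: "we will enroll at least 49 patients to test for superiority of FLARE RT at 80% power and 5% Type I error".
- Section 3.2, Statistical Plan, gives the number tested. The analysis is a "one sample proportionality test using all patients who complete either FLARE RT treatment arm", and the power statement follows: "In our cohort of at least 49 patients, the test is expected to detect a 2yr OS rate improvement", from 57% to 72%, with 5% Type I error, 80% power and a 1% superiority margin.
- The Study Summary has both kinds of number. The Statistical Methodology row says "we will need 49 patients to test for superiority of FLARE RT at 80% power and 5% Type I error". The Number of Subjects row says "The projected enrollment number is 60 in order to meet the study goal of 50 evaluable subjects".

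No section defines evaluable, and none states the count at which accrual closes. Section 7.1 has a toxicity stopping rule, and section 7.2 asks only for accrual reports with a projected completion date.

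**The concern.** One figure serves as two different counts. In section 3.2 and in the Summary's methodology row, 49 is what the test needs. In section 2 it is what the trial will enrol, with the same 80% power attached. The two counts are equal only if every enrolled patient enters the test. The plan does not expect that: the Summary allows for 10 of 60 not being evaluable, and section 5.8 foresees patients being withdrawn from treatment or withdrawing consent.

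At stake is the meaning of the power claim in the primary objective. Closing accrual at 49 enrolled would satisfy section 2 as written, yet the test in section 3.2 would then probably contain fewer than 49 patients.

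**Working it through.** **Inputs.** Null 57%, alternative 72%, Type I error 5%, power 80%, margin 1% and a test in treatment completers (section 3.2); 49 enrolled (section 2); 60 enrolled for 50 evaluable (Summary). Sidedness is not stated. One-sided 5% is assumed first, then two-sided.

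**Reproducing 49.** Normal approximation with variance at the alternative:

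n = 0.72 x 0.28 x (1.645 + 0.842)² / d²

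- d = 0.16 (15 points plus the 1-point margin): n = 48.7, rounded up to 49
- d = 0.15 (no margin): n = 55.4, rounded up to 56
- d = 0.14 (margin applied as superiority, null 58%): n = 63.6, rounded up to 64

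Of the variants tried, including formulas using both null and alternative variances, the arcsine formula and two-sided versions, only d = 0.16 gives 49. It uses the margin in the non-inferiority direction. Either way, 49 comes out as a number analysed, because the formula contains no allowance for loss.

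**From enrolled to analysed.** The only allowance in the documents is 50/60 = 0.833. Assume that it applies to the patients tested in section 3.2.

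- 49 enrolled: 49 x 0.833 = 40.8, about 41 analysed
- To analyse 49: 49 / 0.833 = 58.8, so 59 enrolled, which agrees with the Summary's 60 and not with section 2's 49

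**Power by number analysed.** Power = Φ(d x √(n / 0.2016) − 1.645), one-sided 5%:

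| Analysed | d = 0.16 | d = 0.15 (null 57%) | d = 0.14 (null 58%) |
|---|---|---|---|
| 50 | 80.9% | 76.3% | 71.2% |
| 49 | 80.2% | 75.6% | 70.5% |
| 48 | 79.5% | 74.8% | 69.7% |
| 45 | 77.2% | 72.4% | 67.2% |
| 41 | 73.8% | 68.9% | 63.7% |

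From 49 to 41 the loss is 6.4, 6.7 and 6.7 points. The rows for 48 and 45 show smaller losses of patients, since the 60:50 ratio is only a planning figure. Even in the d = 0.16 column, one patient lost from 49 takes power below 80%.

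**Other tests, 49 to 41 analysed.**

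- One-sided, null and alternative variances: 70.0% to 62.8% against 57%, a loss of about 7 points
- Two-sided 5%, variance at the alternative: 64.7% to 57.1% (d = 0.15) and 58.8% to 51.5% (d = 0.14). Across the two-sided variants the loss is about 7 to 8 points
- Exact binomial, one-sided, against 57%: 60.6% at 49 (35 or more alive, actual size 0.027) and 51.3% at 41 (30 or more alive, actual size 0.025), a loss of 9.3 points, part of it from discreteness

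**The case against.** A reader might infer that the plan forgot to allow for non-evaluable patients, that its sections contradict each other, or that the trial will analyse only 41. The documents support none of these. Section 2 sets a floor, and enrolling 60 satisfies it. The Summary already carries the allowance, and at 60 enrolled its own ratio gives 50 analysed, so nothing is lost. No section says accrual closes at 49.

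The figure of 41 also depends on reading evaluable as completion of a treatment arm. It could instead mean known 2-year survival status or usable imaging. The 60:50 ratio is a planning allowance and not an observed rate of non-completion.

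All of this stands, and it makes the power loss conditional. It does not remove the defect in section 2. The 60 is described as projected, while section 2 is a commitment tied to power, and that power belongs to patients analysed.

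**Conclusion.** The point holds as an inconsistency in how the primary objective states its sample size. Section 2 ties 80% power to an enrolment of 49, whereas 49 is an analysis number in section 3.2.

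The consequence is conditional. If accrual stopped at 49 enrolled, and if evaluable means the completers tested, about 41 would be analysed. Power would fall by about 6 to 7 points under one-sided normal approximations, 7 to 8 two-sided, and about 9 with the exact test. If 60 are enrolled and the allowance proves right, this loss does not arise.

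A reader might also infer that putting 60 in section 2 secures 80% power. It does not. At 50 analysed, one-sided power is about 76% against 57%, and about 71% with the 1% superiority margin. The 80% appears only when the margin is added to the effect. That derivation is a separate issue and is not resolved here.

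**What to change.** In section 2, replace the enrolment sentence with: we will enroll 60 patients so that at least 50 are in the primary analysis set. Use the same two numbers in section 3.2 and in the Summary's Statistical Methodology row.

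Define evaluable as membership of the primary analysis set, and state that accrual does not close at 49 enrolled.

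Attach power to the number analysed and restate it, naming the sidedness and the null. For 50 analysed with a one-sided 5% normal approximation, that is about 76% against 57%, or about 71% against 58% if the margin is kept as superiority.

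The cost is wording in three places. It needs no patients beyond the 60 already projected. The sponsor gives up the option of closing at 49 enrolled and has to report a power below 80% unless the sample size is reconsidered.
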